The primary purpose of this study is to assess the efficacy of larval debridement therapy (LDT) with bagged, sterilized, live, medicinal blow fly (*Lucilia sericata*) larvae (or "BioBags") versus bedside sharp debridement in removing harmful bacteria, biofilm and necrotic tissue from chronic wounds to promote wound healing. Characteristics associated with chronic wound environments will be evaluated through analysis of samples of tissue taken from wound beds before and after both types of debridement. One hundred and forty patients \geq 21 years of age with an open, full thickness wound which is healing by secondary intention (of greater than 8 weeks duration and requires debridement) will be invited to participate. This recruitment number accounts for estimated 10% attrition rate, so final sample number is anticipated to be 128 subjects (64 in each arm). Samples of wound bed tissue and slough tissue (if present) will be collected on Days 0, 4 and 8 or prior to and after each larval debridement intervention or sharp debridement (control). Photos will be taken of the wound bed on Days 0, 4 and 8 or just prior to and after each debridement method. A randomized sampling procedure will place individuals into one of two groups: The intervention group will receive larval debridement therapy once every 4 days for 2 applications (with saline moistened gauze as cover dressing changed daily) and the control group will receive sharp debridement therapy every 7 days for 2 debridements (with wound gel dressing changed daily).

The wound and wound environment will be characterized by assessing wound Matrix Metalloproteinases (MMPs), inflammatory cytokines and the presence of total bacteria, planktonic (free floating) bacteria, and biofilm (sessile) bacteria. Clinicians will be asked to grade the amount of non-viable tissue apparent in the wound bed, appearance of any signs of infection and overall visual appearance of the wound at each visit. Wound size will also be assessed. Subjects will be asked to rate their wound related pain level at each visit before and after the debridement method is applied. Subjects, caregivers and clinicians will be asked to complete a short survey to self-report their perceptions of each method of debridement. Data will be analyzed using bivariate and multivariate methods.

4. **Background:**

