Maggots used in the U.S. for larval debridement therapy are all processed under controlled laboratory conditions and are sterile (both free of disease as well as unable to reproduce). Larval debridement of non-viable tissue within chronic wounds results partly from the proteolytic digestive enzymes liquefying the necrotic tissue, which the larvae then "suck up" (along with bacteria and biofilm) and remove from the wound bed. As such, they are a most efficient way to debride a wound without the pain, bleeding, or inflammatory response associated with sharp debridement.

Unfortunately, current larval debridement methods available in the U.S. have not really addressed the "yuck factor" of loose or free-roaming maggots in open wounds. This may explain why, despite the clinically proven effectiveness of larval therapy to aid in the healing process, many U.S. clinicians do not select this method of wound treatment. Many nurses, doctors, caregivers, and patients alike have voiced an aversion to handling maggots or having to "count the number that go into a wound or come out of a wound" (Cowan et al., 2013). Having to count them is complicated by the fact that when the wound is sufficiently debrided, larger maggots may turn and eat smaller maggots.

Fortunately, there is a brilliant new alternative. A European company, BioMonde, has successfully addressed this issue by manufacturing sterile maggots in a mesh bag called a BioBag. This allows for an aesthetically and psychologically acceptable method of introducing the larval therapy to the wound and removing them all in "one neat package." BioMonde has recently obtained FDA approval for this medical device in the U.S. In addition, several studies validate the comparative effectiveness of these maggots in BioBags versus currently "free range" or loose maggots (Monarch Labs) (Blake et al., 2007). Now that this research has been completed, a randomized controlled trial (RCT) testing larval debridement therapy, also known as "biosurgery" using BioBags versus traditional bedside sharp debridement methods in human subjects with chronic wounds is warranted.

Purpose Statement

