To compare the clinical effectiveness of a self-contained bagged larval debridement therapy (intervention) (BioBag) with bedside sharp debridement (control). The following comparisons will be made: 1) The visual reduction of non-viable tissue in the wound bed of chronic full-thickness lower extremity or diabetic foot ulcers, and 2) The reduction in colony forming units (CFU) of bacterial biofilm in samples taken from the wound bed.

Specific Aim 2

To compare wound characteristics (e.g., inflammatory markers, wound size) in the intervention group (BioBag therapy) and control group (Sharp debridement) over time.

Specific Aim 3

To investigate patient, caregiver and clinician perceptions of larval therapy dressings and bedside sharp debridement using measures of self-reported aesthetics, ease of use, and wound pain.

6. Research Plan:

Research design and methods

Design: A repeated measures, randomized control trial experimental design will be used for this study. Subjects will serve as their own control, in addition to a control group. Initial wound samples will be followed by two subsequent repeated wound samplings approximately four days apart. Informed consent will be obtained prior to all procedures, photo consents will also be obtained for wound photos.

Veteran Site: North Florida South Georgia Veterans Health System

Setting, Sample: A target goal final sample size of one hundred twenty eight adults from the North Florida South Georgia VHS will be recruited (total recruited number anticipated to be ~140 allowing for 10% attrition). Including target of 128 Caregivers and 6 Providers, and accounting for 12 caregivers lost to follow up or 10 subjects who fail screening, the total study recruitment population is 296. Wound providers and clinicians who care for lower extremity or diabetic foot ulcers will be provided with a "Provider Study Flyer" which gives a brief description of the study with inclusion/exclusion criteria listed (to remind the Provider to approach potentially eligible patients with Research Team Contact

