Measurement of IL6. Using techniques such as ELISA and fluorescence resonance energy transfer (FRET) assay methodology, the levels of active IL6 will be calculated and reported.

Methods for Data Collection & Data Management

Variable	Significance	Sampling time	Source	Specific Aim
Age	Demographic	Baseline	EHR	n/a
ABI	Exclusion criterion	Baseline - enrollment	ABI done after ICF	n/a
% nonviable wound tissue	Appearance of wound bed	Baseline Day 0 and Day 8	Provider assessment	Aim 1
Quantitative Cultures (planktonic and biofilm)	Microbial identification	Day 0 (pre-test), + Day 4 and Day 8	Wound samples	Aim 1
Wound Size in cm ² (volume: L x W x D)	Descriptive	Baseline Day 0 and Day 8	Wound measurements	Aim 2
Interleukin 6	Marker of inflammation	Day 0 (pre-test), + Day 4 and Day 8	Wound sample (fluid and/or tissue)	Aim 2
Matrix metalloproteinases (MMP-2 and 9 equivalent)	Elevated MMPs associated with non-healing wounds	Day 0 (pre-test), + Day 4 and Day 8	Wound sample (fluid and/or tissue)	Aim 2
Perceptions of therapy	Perceptions of debridement	Day 0 (pre-test) + Day 8	Patient, Caregiver & Clinician Surveys	Aim 3

Survey Methods

Subjects will be asked to complete a paper survey at Day 0, Day 4 and Day 8 of the study, querying the patient's perceptions of: wound pain, satisfaction with most recent/current wound care method, ease of

care, effectiveness of most recent wound treatment, aesthetics of current wound treatment and toward sharp debridement and maggots for wound care.

Caregivers and wound clinical providers will be asked to complete a paper survey at Day 0 and Day 8 of the study (if wound clinician is caring for more than one study subject, they will be asked to complete a survey at day 0 of first subject, day 8 of first subject and 3 months later or at completion of the study for each type of debridement), querying them about their perceptions of what the patient's experience was regarding the most recent wound debridement methods as well as satisfaction with most recent/current wound care method, ease of care, effectiveness of most recent wound treatment, aesthetics of most current wound treatment and toward sharp debridement and maggots for wound care.

Data Analysis

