The main study PI will review the collected data monthly during sample collection to identify any possible breach of the study protocol, including incorrect consent procedure or data storage. This study will be monitored by the University of Florida IRB and the NF/SG VHS R&D Committee as well as the Research Compliance Officer, who have institutional responsibility to oversee the progress of research studies and the safety of study participants. The PI has the responsibility to promptly report any adverse event or breach of the study protocol. Should any adverse event or breach of protocol occur, they will be reported in accordance with the IRB standard operating procedures enforced by the IRBs at University of Florida, North Florida Regional Medical center, and the NF/SG VHS research Offices. All of the research team members will be required to pass the mandatory training programs for human subject research and be certified by the IRB for conducting this study.

Inclusion of women, minorities and/or children: Efforts will be made to recruit women and minority patients.

7. Possible Discomforts and Risks:

Adequacy of Protection from Risk

Potential Risks: The risks to human subjects associated with this study are minimal related to the collection of wound samples, since these samples will be collected by the PI or patient's wound care clinicians. The risks related to the debridement techniques are also minimal since bedside sharp debridement is typically a standard of care in these patients with lower extremity or diabetic foot ulcers and the risk of larval debridement therapy is considered to be less than that of sharp debridement. Potential risks related to sharp debridement, and to a lesser extent, to larval debridement, may include: bleeding, pain, increased wound draining, infection, increased wound odor, and in the case of larval

debridement, a “crawling” sensation in wound. Potential risks related to subject, caregiver and wound clinician participation with the study survey component are minimal, due to the fact that no sensitive information is being collected.

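### Apart from pain, no listed harm and no adverse-event count has a variable-table row or a by-arm analysis, so the trial could report benefit with almost no comparative harm data

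*Combined protocol and SAP*

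**What the plan says.** Section 7 (Possible Discomforts and Risks) calls the risk of the debridement techniques minimal, partly because "the risk of larval debridement therapy is considered to be less than that of sharp debridement". It lists "bleeding, pain, increased wound draining, infection, increased wound odor" as possible with either method, to a lesser extent with larvae, and adds a crawling sensation for larvae only. Section 4 (Background) says larvae debride "without the pain, bleeding, or inflammatory response associated with sharp debridement".

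The plan collects some of this. The opening summary asks clinicians to grade "appearance of any signs of infection and overall visual appearance of the wound at each visit", and adds: "Subjects will be asked to rate their wound related pain level at each visit before and after the debridement method is applied". Aim 3 in Section 5 compares perceptions "using measures of self-reported aesthetics, ease of use, and wound pain", and Survey Methods puts "perceptions of: wound pain, satisfaction with most recent/current wound care method" in the patient survey.

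The variable table in Section 6 has rows for age, ABI, nonviable tissue, quantitative cultures, wound size, interleukin 6, MMPs and perceptions of therapy. Data Analysis promises a general descriptive summary and then gives between-arm methods for Aims 1, 2 and 3 only.

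Under the Data and Safety Monitoring Plan, the main investigator is to "review the collected data monthly during sample collection to identify any possible breach of the study protocol". The same paragraph requires prompt reporting of adverse events under IRB procedures, and gives the IRB, the R&D Committee and the Research Compliance Officer responsibility for participant safety.

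**The concern.** Section 7 names the harms that matter, but the parts of the plan that decide what is recorded and compared do not pick them up. The infection grade is the clearest case: it is requested at each visit, yet it has no table row, no assigned aim and no named method. Bleeding, drainage and odor have no scheduled question at all.

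Section 4 describes the trial as the first US clinical test of this device. It foresees results being applied in practice, possibly with a nurse or informal caregiver applying the larvae at home. A result showing better debridement would then be read with almost no comparative information on infection or bleeding.

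A participant harmed in one arm could also be removed at the provider's discretion for clinical reasons, which Section 6 allows, and appear only as attrition. Harms that were not asked about in the same way in both arms cannot be recovered afterwards.

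**Working it through.** **1. Trace each harm through the plan.**

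| Harm | Listed in Section 7 | Collected | Row in variable table | Named by-arm method |
|---|---|---|---|---|
| Pain | Yes | Each visit; patient survey | Through the perceptions row | Yes, Aim 3 |
| Infection | Yes | Clinician grade, each visit | No | No |
| Bleeding | Yes | No scheduled item | No | No |
| Increased drainage | Yes | No scheduled item | No | No |
| Odor | Yes | No scheduled item | No | No |
| Crawling sensation | Larvae only | No scheduled item | No | Not applicable |
| Adverse events | – | Reported as they occur | No | No |

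One harm common to both arms (pain) is carried through to a comparison. Four are not. The survey forms are in appendices that were not available, so an item on odor, drainage or crawling may exist there. Neither the table nor Data Analysis names one.

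**2. The plan's own sample size.** Section 6 gives 64 per arm for a standardized effect of 0.50, two-sided alpha .05 and at least 80% power. The normal approximation is n = 2(1.96 + 0.8416)² / 0.50² = 62.8, so 63. The t-test calculation gives 63.77, so 64, with power 0.801 at 64. The figure reproduces. It concerns clinical effectiveness; no sample size is given for harms.

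**3. Precision for a harm at that size.** The documents give no harm rates, so the rates below are assumptions. With the same true rate p in both arms and 64 per arm, the 95% half-width for the risk difference is 1.96 × √(2p(1 − p)/64):

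- p = 5%: 7.6 percentage points
- p = 10%: 1.96 × √(0.18/64) = 10.4 points
- p = 20%: 13.9 points

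If all 140 recruited are treated, 70 per arm, the 10% case becomes 1.96 × √(0.18/70) = 9.9 points.

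With zero events among 64 in an arm, the one-sided 95% upper bound is 1 − 0.05^(1/64) = 4.6%. The upper limit of a two-sided 95% interval is 1 − 0.025^(1/64) = 5.6%.

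**4. Power if harms were tested.** Two-sided .05, 64 per arm, assumed rates:

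| Rates | Fisher exact power | n per arm for 80% power (normal approximation) |
|---|---|---|
| 5% vs 2.5% | 3% | 906 |
| 10% vs 5% | 10% | 435 |
| 20% vs 10% | 27% | 199 |

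A significance test on these harms would rarely be informative, and a non-significant result could be misread as equal safety. Intervals are the appropriate output.

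**5. Timing of the review.** Participation lasts 8 days. With even enrolment and a 30-day cycle (both assumptions), (30 − 8)/30 = 73% of participants finish before the next review. A monthly look therefore protects few current participants. Its use is to show a pattern building up across participants, and for that it has to show events by arm.

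**The case against.** A reader might infer that the trial compares no harm at all. The documents do not support that. Pain is a listed risk and an Aim 3 outcome with a named analysis. Interleukin 6, an inflammation marker, is compared under Aim 2. Of the three things that Section 4 says larvae avoid, only bleeding goes unmeasured.

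A reader might also infer that the trial sets out to show lower larval risk and fails to test it. The Section 7 sentence is a premise for calling the risk minimal; none of the three aims takes it up as a hypothesis.

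Nor can one infer that adverse events go unseen. Prompt reporting is required and three bodies have safety responsibility. The text is silent on whether any of them sees events by arm, and their own procedures are not in the documents. Section 4 also reports FDA approval and more than 40,000 British and European treatments a year.

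The table is not an exhaustive list either: gender and smoking are recorded without a row. Aim 2 gives its wound characteristics only as examples, so the infection grade might be analysed there.

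These points stand, and they make this a gap in specification and reporting rather than an absence of safety oversight. They do not close it. A general promise of descriptive statistics does not commit anyone to a by-arm harm summary, and an open list cannot supply data on bleeding, drainage or odor that no form is stated to collect. The low power is also a fair objection, but to hypothesis tests rather than to counts with intervals.

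**Conclusion.** The point holds in this form: apart from pain, no harm listed in Section 7 for both methods, and no adverse-event count, has a table row or a by-arm analysis, and the only review with a stated frequency is aimed at protocol breaches. Followed as written, the trial could report a debridement benefit with almost no comparative harm data. Except for pain, it could neither confirm nor refute the premise that larval risk is lower.

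Closing the gap would give modest precision: about ±8 to ±14 percentage points at 64 per arm for equal rates of 5% to 20%, which are assumed. That is enough to describe harms and to reveal a large imbalance, but not to establish lower risk. The change should be made, but it does not call the design into question. The conclusion assumes that the unseen survey forms contain no analysed harm items beyond pain.

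**What to change.** 1. Add the existing infection-sign grade to the variable table, plus yes/no items for bleeding, increased drainage and odor. Ask them in identical words in both arms at Days 4 and 8, each covering the whole interval since the previous assessment, so that the Day 7 sharp debridement is included. Record crawling sensation in the larval arm only, descriptively.
2. Add to Data Analysis a table of counts by arm and risk differences with 95% confidence intervals, in all treated participants, including those removed before Day 8. Use a method that remains valid with zero or few events. Present these as descriptive results without significance tests.
3. Add cumulative adverse events by arm to the existing monthly review, and send the summary to the monitoring bodies already named.
4. Limit any safety statement to what the intervals support. State two limits: the clinicians assessing these items know the treatment, and Day 8 falls 24 hours after the second sharp debridement but at bag removal in the larval arm, so the two assessments do not follow treatment by the same interval.

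The cost is a few checkboxes at existing visits, one table and one added review item. No new visits are needed and the sample size does not change.
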